3.2 Statistical Analysis

Descriptive statistics will be provided for all variables collected including patient demographics, numbers progressing to requiring more oxygen, and all secondary outcomes. Categorical variables will be summarized as counts and percentages. All continuous variables will be summarized as means \pm the standard deviation where normal or median and 25th, 75th percentiles if not normal. The minimum and maximum will also be provided.

Analysis Sets: Data analysis will be performed on a full analysis set (FAS), a per protocol set (PPS), an intent-to-treat (ITT) set, and a safety analysis (SA) set.

The FAS will be used for the primary analysis. The FAS will consist of all randomized subjects who receive at least one naltrexone/placebo treatment. All analyses using the FAS will group participants according to randomized treatment in an intent-to-treat analysis.

The PPS will be used for a supportive analysis and will be defined as all subjects included in the FAS who do not have any significant protocol deviations. All analyses using the PPS will group subjects according to treatment the subject actually received.

The safety data set will include all subjects with all safety data but will lack any outcome data. This data set will be used for reporting to the internal safety committee.

Missing Data: We will evaluate the potential impact of any missing data on analyses before deciding how to include missing data. Missing data will not be replaced by substitutions or imputation as long as the percent missing for any of the variables is less than 5%. Should the percent missing increase above 5%, we will use multiple imputation to replace missing data and conduct any analyses outlined below.

Primary Outcome: Progression to requiring more oxygen will be the primary outcome, and we will compare the percent patients progressing between the two arms of this study. The primary hypothesis is that the percent progressing for those in the naltrexone arm will be less than the percent progressing in the placebo arm. We will use the Pearson chi-squared test this hypothesis using a one-sided type 1 error rate of 0.05. We will also estimate the difference in proportion progressing using a Bayesian approach with independent Jeffrey's priors for both groups and numerical integration to obtain the credibility interval for the difference in proportions.

Sample Size Determination: We assumed that 20% of patients admitted to the hospital will show progression to requiring more oxygen, and that we want to detect if naltrexone reduces the progression rate to no more than 10%. With these assumptions, a sample size of 154 per arm (308 total) is required to have 80% power based on a two-sample t-test, using PASS 16.

Secondary Outcomes: To examine the potential impact of ketamine on mortality, we will use the chi-squared test to evaluate the hypothesis that mortality is reduced in the naltrexone arm. We will also estimate the difference in proportions using the Bayesian approach noted above. We will use a type 1 error rate of 0.05 for this secondary outcome.

For all remaining secondary outcomes, we will estimate the difference between the two arms and not test for differences between the two arms since these data will be used in planning future studies. For dichotomous outcomes (renal failure, liver failure, cytokine storm, and ARDS), we will use the Bayesian approach discussed for estimating the difference in proportions. We will use generalized linear models to estimate the difference in durations (number of days in ICU, number of days on a ventilator, and length of stay), evaluating the distribution to use based on the data. We will consider using the Poisson, negative-binomial, and normal distributions. We will use a Bayesian approach, using a flat prior on the difference in means parameter. We will calculate 99% credibility intervals for all of these secondary outcomes given the multiple outcomes being examined.

For statistical analysis the biostatisticians and Data analytics teams at Beaumont ([name] and [name]) will pull patients who were not on SINK, had COVID-19 with as close to a direct match to patients with similar profiles who were treated on the SINK study. The match to the patients on SINK will aim to compare the outcomes of the two groups, to see if there is a difference in the outcomes. The evaluation is a chart analysis aimed at focusing on the outcomes of the study.

Safety Measures:

There will be a full DSMB consisting of an infectious disease physician, two additional physicians, a biostatistician, and a pharmacist. A medical monitor will review safety data weekly (+/- 7 days). Adverse event summaries will be emailed to the committee weekly. The DSMB will meet monthly but can choose to modify that schedule based on patient recruitment levels. At a minimum they will have quarterly meetings no matter what the level of recruitment is. When 20 patients (from the open-label arm) have been placed on ketamine enrollment will be held. The DSMB will review the data for safety of using ketamine. The DSMB will then present their findings to the IRB to determine if protocol revisions are necessary and when enrollment may resume.

With the completion of the initial safety review, going forward the DSMB will formally meet at least each quarter with the option to meet earlier if enrollment is found to be high enough to warrant it. There are no further automatic holds to enrollment. PI and study team will monitor study patients at least daily or more frequently due to their severe illness risks.

4. Future Directions

If the **SINK COVID-19** study is successful we plan to develop a large multi-center trial to confirm the results on a larger scale.

- 2 - Johns Hopkins Coronavirus Resource Center, <https://coronavirus.jhu.edu/map.html>, accessed 3/23/2020 at 12:34 AM.
- 3 - <https://www.clickondetroit.com/news/local/2020/03/18/man-at-wayne-county-hospital-is-michigans-first-confirmed-coronavirus-death> , accessed 3/23/2020 at 6:50 PM
- 4 - <https://www.cdc.gov/coronavirus/2019-ncov/symptoms-testing/symptoms.html>, accessed 3/23/2020 at 1:16 AM
- 7 – McCarthy A. U.S. COVID-19 Fatality Rate Steady: About 1 Percent. *National Review* ePub: 20 March 2020.

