therapeutics such as discussed above, the addition of immunomodulators to the treatment regimen appear to be an excellent choice for agents which can reduce the pathogenicity of this disease by reducing the dysregulation of autoimmunity which is destructive of normal tissue and when unchecked rapidly leads to mortality. The use of naltrexone will be done in a randomized, double blinded manner whereas the use of ketamine will be unblinded and given as a rescue agent should a patient progress. Additionally should a patient be ineligible for the randomized portion of the study due to already being in stage 2B or stage 3 of the disease, they will be given the opportunity to enter the trial to receive ketamine without being randomized to naltrexone vs placebo.

3. Approach

Specific Aims

Aim 1: Determine whether treatment with low dose naltrexone, 4.5 mg by mouth daily, reduces progression of patients with COVID-19 from stage 1 or stage 2A to stage 2B or stage 3.

- 1.1: Determine the percentage of patients on naltrexone who proceed to requiring advanced oxygenation (hiflo nasal canula, non-rebreather, CPAP, BIPAP, or intubation)**
- 1.2: Determine the impact of naltrexone on development of renal failure, liver failure, cytokine storm, and ARDS.**
- 1.3: Determine the impact of naltrexone on mortality, length of stay, admission to ICU, length of stay in ICU, intubation, length of intubation, and time till recovery.**

Aim 2: Determine if ketamine can improve mortality in patients who progress the need for advanced oxygenation.

- 2.1: Determine the impact of ketamine on development of renal failure, liver failure, cytokine storm, and ARDS.**
- 2.2: Determine the impact of ketamine on mortality, length of stay, admission to ICU, length of stay in ICU, intubation, length of intubation, and time till recovery.**

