3.1 Research Design

To date we have over 100 patients admitted to Beaumont, Royal Oak in the space of 1 week with about 25% needing to be admitted to the ICU. Of the first 101 patients admitted 25 ended up admitted to the ICU, 12 to the advanced COVID Unit (medical progressive care), and 64 to COVID general floor, these numbers can fluctuate and those in the COVID units can still progress to the floors. Approximately 70 of the 101 patients were treated with hydroxychloroquine and azithromycin.

This is a prospective, single center, randomized, double blinded study of naltrexone for the treatment of COVID-19 with an open label extension using ketamine as a rescue drug for patients who progress in their disease. We plan to recruit up to 500 patients. All COVID positive patients will be screened by the following criteria:

Inclusion	Exclusion
Positive for COVID -19	Known allergy to naltrexone
Admitted to Royal Oak	Known allergy to ketamine
Age \geq 18	Diagnosis of schizophrenia or acute psychosis
On \leq 6L Oxygen by nasal cannula ^A	Pregnancy
	On chronic high dose opioids > 90mg morphine mg equivalence
	Use of naltrexone or Vivitrol within 90 days

A – If on more than 6L oxygen by NC patient can be enrolled as a non-randomized patient directly into the ketamine rescue group.

If eligible the patient or their LAR will be approached for inclusion in the study. Given the nature of the pandemic and the shortage of personal protective equipment all consenting will take place over the phone in the presence of a witness as per IRB emergency safety policy during COVID19.

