If at any point a patient requires advanced oxygenation (hiflo nasal cannula, non-rebreather, CPAP, BIPAP, or intubation) for more than 15 minutes they will then be given ketamine as a rescue treatment and remain on the Naltrexone or placebo. Ketamine will initially be given at a dose of 0.15 mg/kg based on total body weight (max 20 mg) every 6 hours (+/- 1 hour) by intravenous piggyback over 30 minutes. Ketamine will continue until the patient is deemed stable for low level oxygen. If the patient relapses after the ketamine is stopped they can be restarted on the ketamine. If the patient continues to worsen or displays evidence of cytokine storm (elevated markers of inflammation, evidence of ARDS, continuous fever) the dose of ketamine will be increased to 0.3 mg/kg IV every 6 hours (max 30 mg). The dose of ketamine can be reduced back to 0.15 mg/kg at the clinical decision of the physician investigators. If a patient has issues with hypertensive emergency the dose of ketamine can be held until the hypertensive emergency is controlled.

In addition, a patient can receive ketamine if they are not yet on advanced oxygenation if the investigating physician feels they are moving toward cytokine storm based on the markers of inflammation and clinical factors such as worsening imaging and unrelenting fever. If a patient transitions to comfort care the patient will remain in the study for data collection purposes. Study medications may be held if requested by the clinical team, patient, LAR or family.

Patients who at screening are already requiring advanced oxygen can be consented and enrolled in the study and immediately will skip the randomization and be placed on naltrexone and receive ketamine as the starting treatment in an open label manner.

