All patients will have the following labs drawn on a daily basis for the first 5 days after randomization and then weekly while in the hospital: IL-6, CBC with differential, CMP, Triglycerides, Ferritin, Fibrinogen, ESR, CRP, LDH, CK, Troponin, and D-dimer. An additional IL-6 will be drawn prior to the first dose of study drug to establish a baseline. In addition if a patient is placed on ketamine these labs will be drawn for the 5 days following initiation of ketamine and then return to once a week. These labs are measures of general medical status, renal status, liver status, and markers of inflammation. The use of these labs is 2 fold, they may be used up front to help determine when a patient should have the dose of ketamine escalated and they will be reviewed retrospectively for the research to determine impact of

the study drugs. IL-6 in particular will only be looked at retrospectively as it is a send out test and the length of time to get results is 3-5 days. Each patient will have the following vital signs from the prior calendar day and related data recorded on a daily basis: maximum temperature, minimum temperature, maximum heart rate, minimum heart rate, maximum blood pressure (based on mean arterial pressure), minimum blood pressure (based on mean arterial pressure), maximum oxygen patient is on and the method of delivery, minimum oxygen patient is on and the method of delivery, maximum respiratory rate, minimum respiratory rate. The nurses and physicians participating in this study will also be looking for progression of oxygen requirements whenever they access the chart and the floor staff will be instructed to call the study team immediately for consideration of ketamine rescue.

After the first five days the labs will be collected once a week (every 7 days +/-1 day) until discharge. Any of these labs drawn by the treatment team will be collected if they match the timeframe of the study labs additional labs will not need to be ordered for the study.

For all patients we will collect medical history specifically including what COVID-19 symptoms were present and for how long, the date and time of the positive COVID test and what lab it was run at, demographics, concomitant medications on a daily basis, and any available cardiac markers including CK, troponin, myoglobin and echocardiography results.

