3.2 Measurements of Outcomes

Primary Outcome Measure:

1. Progression of oxygenation needs

Count of participants initially presenting with mild/moderate disease who progress to requiring advanced oxygenation (high flow nasal canula, non-rebreather, continuous positive airway pressure (CPAP), bilevel positive airway pressure (BIPAP), or intubation)

[Time Frame: up to 1 month]

Secondary Outcome Measure:

2. Renal failure

Count of participants who develop or experience worsened renal failure as defined by RIFLE criteria, a 5-point scale where the categories are labeled: Risk-Injury-Failure-Loss-End stage renal disease, with Risk being the least severe and End stage renal disease being the most severe. The criteria for determination of stage are factors of serum creatinine and urine output. Numbers of participants worsening one or more RIFLE stages will be reported.

[Time Frame: up to 1 month]

3. Liver failure

Count of participants who develop or experience worsened liver failure as defined by serum transaminases five times normal limits

[Time Frame: Daily times 5, then weekly]

4. Cytokine Storm

Count of participants who develop cytokine storm as measured by elevated markers of inflammation (elevated D-dimer, hypofibrinogenemia, hyperferritinemia), evidence of acute respiratory distress syndrome (ARDS) measured by imaging findings and mechanical ventilator requirements, and/or continuous fever (≥ 38.1 ° Celsius unremitting)

[Time Frame: 1 month]

5. Mortality

Count of participants who die from COVID-19

[Time Frame: up to 1 month post hospital discharge]

6. Length of hospital stay

Length of hospital stay in days

[Time Frame: 1 month]

7. Intensive Care Unit (ICU) admission

Count of patients admitted to the ICU at any time during index hospitalization

[Time Frame: 1 month]

8. Intensive Care Unit (ICU) duration

Length of ICU stay in days

[Time Frame: 1 month]

9. Intubation

Count of participants requiring intubation

[Time Frame: 1 month]

10. Intubation duration

Length of intubation, measured in days

[Time Frame: 1 month]

11. Time until recovery

Time measured in days from hospital admission to determination patient is stable for discharge

[Time Frame: 1 month post hospital discharge.]

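### Does the primary event need a minimum duration and a cannula-flow limit before the chi-squared test can be run?

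*Combined protocol and SAP*

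**What the plan says.** Section 3.2, Measurements of Outcomes, gives the primary outcome as "Count of participants initially presenting with mild/moderate disease who progress to requiring advanced oxygenation (high flow nasal canula, non-rebreather", then CPAP, BIPAP or intubation, over up to 1 month. Aim 1.1 in section 3 uses the same device list. Neither states a minimum time on the device or a flow in litres.

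Section 3.2, Statistical Analysis, is looser. Its Primary Outcome paragraph says "Progression to requiring more oxygen will be the primary outcome, and we will compare the percent patients progressing between the two arms", and its opening paragraph promises descriptive statistics for "numbers progressing to requiring more oxygen, and all secondary outcomes". The Sample Size paragraph attaches its 20% versus 10% to the same short phrase.

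Two other places draw similar lines for other purposes:

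- **Rescue (section 3.1).** A patient who "requires advanced oxygenation (hiflo nasal cannula, non-rebreather, CPAP, BIPAP, or intubation) for more than 15 minutes they will then be given ketamine". Section 2.4 summarises this as "the use of ketamine will be unblinded and given as a rescue agent should a patient progress".
- **Entry (section 3.1).** Patients on 6 L or less by nasal cannula are randomised. Note A to the criteria says: "If on more than 6L oxygen by NC patient can be enrolled as a non-randomized patient directly into the ketamine rescue group". Later the section describes the same open-label route without a litre figure: "Patients who at screening are already requiring advanced oxygen can be consented and enrolled in the study and immediately will skip the randomization".

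The daily record in section 3.1 includes "maximum oxygen patient is on and the method of delivery, minimum oxygen patient is on and the method of delivery".

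**The concern.** Read literally, the phrase in the analysis section would count a rise from 2 L to 4 L by cannula, which is not on the device list. Even if the phrase is shorthand for the listed devices, two kinds of randomised patient look unclassified. One uses a listed device for less than 15 minutes: an event under the outcome definition, but short of the rescue trigger. The other rises to, say, 8 L by ordinary cannula: beyond the level that bars randomisation, yet an event only if high-flow cannula is taken to include any flow above 6 L.

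This is the only primary endpoint. If such cases were settled after the data had been seen, the event count would be open to choice, and a result near the significance limit can turn on one patient. The 20% control rate would also have no definite event behind it.

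**Working it through.** **1. What each passage does**

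| Place | Purpose | Devices | Minimum time | Cannula flow |
|---|---|---|---|---|
| Primary Outcome Measure; Aim 1.1 | Defines the event | Listed | None | None |
| Section 3.1, rescue | Starts ketamine | Same list | More than 15 minutes | None |
| Section 3.1, criteria and note A | Decides randomisation | Nasal cannula | None | 6 L |
| Section 3.1, open-label entry | Same route as note A | Advanced oxygen, in words | None | None |
| Statistical Analysis | Names the outcome to be tested | None | None | None |

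Only the first row is a definition of the endpoint.

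*Duration.* With no minimum stated, any required use of a listed device within the window counts. That rule is complete, and the daily maximum oxygen with its delivery method is enough to apply it. Rescue and endpoint are in any case separate: section 3.1 also allows ketamine for patients not yet on advanced oxygenation whom the investigator judges to be heading toward cytokine storm.

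*Flow.* Entry and outcome limits need not meet. As written, an ordinary cannula is not on the list. The two descriptions of the open-label route suggest that the authors may equate more than 6 L with advanced oxygen, but no sentence carries this into the outcome definition. This is the one point left open.

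**2. The plan's sample size**

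Inputs from Statistical Analysis: 20% versus 10%, one-sided 0.05, 80% power.

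n = (1.645 + 0.842)² × (0.20×0.80 + 0.10×0.90) / 0.10² = 6.185 × 0.25 / 0.01 ≈ 154.6 per arm.

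The pooled formula gives 157 and a t-test with averaged variance 156. Exact binomial power at 154 is 80.1%. The stated 154 stands.

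**3. Sensitivity of the test to reclassification**

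z = (a − b)/154 ÷ √[2p(1 − p)/154], with p = (a + b)/308, where a and b are the placebo and naltrexone event counts. The critical value is 1.645.

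- Planned rates: 0.20 × 154 ≈ 31 and 0.10 × 154 ≈ 15. p = 46/308 = 0.149; z = 0.1039/0.0406 = 2.56; one-sided p-value 0.005.
- Equal numbers added to both arms: z never falls below 1.82.
- A share of events removed from both arms (for example, brief use): 10% leaves 27.9 versus 13.5, z 2.41; 30% leaves 21.7 versus 10.5, z 2.09.
- A share of non-progressors (123 placebo, 139 naltrexone) added as events: 2% gives 33.5 versus 17.8, z 2.40; 10% gives 43.3 versus 28.9, z 1.94; 20% gives 55.6 versus 42.8, z 1.56.

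The shares are assumptions, since the documents give no counts. Significance at the planned effect is lost only when a large share, somewhere between 10% and 20% of all non-progressors, becomes events.

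**The case for a change.** The strongest case is that pointing the analyst to the outcome section does not classify the 8 L patient, and that a sole primary endpoint deserves an explicit rule. Near the limit one patient matters: 31 versus 20 events gives p = 0.046, and 31 versus 21 gives p = 0.064. Power also depends on the event counted. At 154 per arm it is about 79% by the normal approximation; it falls to 75% if 10% of events in both arms drop out, and to 68% if 5% of non-progressors are added.

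Part of this stands. The flow question is unanswered, the wording in the analysis section is careless, and the 20% has no stated source. But results that turn on one patient show how any binary test behaves near its limit; they do not measure this gap. Shifts confined to one arm are not what double-blind allocation to naltrexone or placebo would be expected to produce. The power losses describe other events that the sponsor might have chosen; they do not show that the listed-device event is wrong. Nothing in the plan says that the rule would be settled after unblinding.

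On the 20%, section 1.4 offers a likely origin: it states that 20% progress to stage 2B, and Aim 1 is about progression to stage 2B or 3. That figure concerns infected people, whereas the sample size speaks of hospital admissions, so the link is plausible but not proven.

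**Conclusion.** No change to the plan follows. The endpoint has a usable definition, stated twice in agreement, and the looser phrase in the analysis section is best read as shorthand for it. The 15-minute and 6 L figures serve rescue and entry, and neither conflicts with the outcome definition. The gap that remains, ordinary cannula flow above 6 L, is one of detail. An analyst who follows the device list as written has a rule that applies equally to both arms.

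The number of patients affected is unknown. At the planned event counts, equal additions to both arms leave z at 1.82 or more, and removing up to 30% of events from both arms leaves it at 2.09 or more. This rests on three assumptions: the device list governs the count, borderline cases are classified without knowledge of arm, and the effect is near the planned 20% versus 10%. The two descriptions of the open-label entry route differ in wording; reconciling them is for the sponsor, and this review takes no view on which threshold is right. The 154 per arm is correct for its stated inputs.

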Patients who consent will be randomized to one of 2 arms: Arm 1 – low dose naltrexone 4.5 mg by mouth per day (can be given via NG tube if needed). Arm 2 – placebo by mouth per day. Treatment will be for 30 days past discharge. If the patient develops severe insomnia or shows symptoms of opioid withdrawal the dose of naltrexone can be decreased to 3 mg by mouth per day. If the patient continues to demonstrate issues on the 3 mg reduced dose of naltrexone the dose can be further reduced to 1.5 mg by mouth per day or held temporarily if needed. Reasons it may need to be held include if it is interfering with sedation, due to the unique issues with sedation in COVID-19 often requiring large amounts of opioids. Even low dose naltrexone seems to interfere with sedation in some of the patients. Since opioids, particularly fentanyl, are stored in fat, a patient who is starting on study who has been on opioid based sedation for 3 days or more can be started on a reduced dose of naltrexone (as above) or the naltrexone can be held from start and only ketamine used until their sedation is weaned to levels where clinically it is felt the naltrexone will no longer cause issues with sedation or signs of withdrawal. A patient should have naltrexone started by the time ketamine is no longer needed.

Imaging data, flowsheets, and medical notes will be abstracted to generate a daily summary of the patient's status to determine renal failure, liver failure, cytokine storm, ARDS, improvement vs progression of disease, need for advanced oxygenation, ICU status, and mortality.

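### The primary test is valid but unadjusted; stratifying it by oxygen level at randomisation costs almost nothing, may add power and guards against chance imbalance

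*Combined protocol and SAP*

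**What the plan says.** - **Primary test** (section 3.2, Statistical Analysis): "We will use the Pearson chi-squared test this hypothesis using a one-sided type 1 error rate of 0.05". A Bayesian difference in proportions with independent Jeffreys priors accompanies it. Neither uses a covariate or stratum.
- **Randomisation** (section 3.1): "Patients who consent will be randomized to one of 2 arms". No stratification factor is named.
- **Eligibility** (section 3.1, inclusion table): the upper limit for randomised patients is "6L Oxygen by nasal cannula". Patients above it go to the open-label group.
- **Outcome** (section 3.2, Measurements of Outcomes): "Count of participants initially presenting with mild/moderate disease who progress to requiring advanced oxygenation". The Statistical Analysis section words it differently: "Progression to requiring more oxygen will be the primary outcome".
- **Oxygen data** (section 3.1): "Each patient will have the following vital signs from the prior calendar day and related data recorded on a daily basis". The list includes maximum and minimum oxygen with delivery method, but not the level at the moment of randomisation.
- **Size**: 154 per arm for 20% versus 10% and 80% power (Sample Size Determination); section 3.1 adds "We plan to recruit up to 500 patients".

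**The concern.** A patient on 5 L is closer to advanced oxygenation than one on room air, so starting oxygen is a natural candidate for a strong baseline predictor. It is already checked for eligibility, yet the plan does not use it. Two things follow if it predicts progression. Some power is left unused at the same sample size. And if randomisation happens to put more high-oxygen patients in one arm, the primary estimate and p-value carry that difference uncorrected. An adjustment chosen only after such an imbalance was seen would be open to challenge as post hoc.

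**Working it through.** **1. Reproduce the plan's figure.** Inputs from Sample Size Determination and the primary-outcome paragraph: 20% versus 10%, one-sided 0.05, 80% power. With the unpooled variance, n = (1.645 + 0.842)² × (0.20×0.80 + 0.10×0.90) / 0.10² = 6.18 × 0.25 / 0.01, or 155 per arm. The pooled-variance formula gives 157. The stated 154 agrees within rounding. Exact enumeration of the one-sided Pearson test at 154 per arm gives 80.1% power, and a size of 5.01% to 5.09% for common rates of 10% to 25%. The planned test is sound.

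**2. Assumptions for the alternative.** The documents give neither the mix of starting oxygen nor risk by level. Assumed mix: 40% room air, 35% up to 3 L, 25% on 4-6 L. Placebo risks in the three bands are chosen so that the overall rate is about 20%, with a constant odds ratio bringing naltrexone to 10% overall. Allocation is unstratified and 1:1.

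**3. Tests compared.** The unadjusted pooled z test, against the Cochran-Mantel-Haenszel (CMH) statistic without continuity correction:

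Z = Σ(a₀ₖ − n₀ₖmₖ/Nₖ) / √Σ[n₀ₖn₁ₖmₖ(Nₖ − mₖ) / (Nₖ²(Nₖ − 1))]

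Here a₀ₖ is placebo events in band k, mₖ all events, n₀ₖ and n₁ₖ the arm sizes, and Nₖ their sum. There were 200,000 simulated trials per scenario.

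**4. Power at 154 per arm.**

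| Placebo risk by band | Odds ratio, 4-6 L vs room air | Unadjusted | Stratified | Change (points) |
|---|---|---|---|---|
| 20/20/20% | 1.0 | 80.1% | 79.8% | -0.3 |
| 15/20/28% | 2.2 | 80.1% | 80.2% | +0.1 |
| 10/20/35% | 4.8 | 80.1% | 81.4% | +1.3 |
| 5/20/44% | 14.9 | 80.0% | 83.7% | +3.7 |
| 3/16/53% | 36.5 | 80.2% | 86.8% | +6.6 |

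Overall size was 4.97% to 5.11% for both tests. With a reversed gradient the change is +0.6 (28/18/10%) and +2.3 (34/15/5%). Across three other mixes (60/30/10, 20/40/40, equal thirds) it is -0.4 to +7.7. A separate run with two equal strata gave -0.2 with no gradient and +3.0 at an odds ratio of 8.

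**5. How often imbalance arises.** The difference between arms in the share on 4-6 L has standard deviation √(2 × 0.25 × 0.75 / 154) = 4.9 points. A gap of 5 points or more means at least 8 patients (8/154 = 5.2 points). It occurs in about 16% of trials in each direction, 32% in all.

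**6. What such an imbalance does.** At 10/20/35%, the other two bands average (0.40×10 + 0.35×20)/0.75 = 14.7%. If the displaced patients come from those bands in proportion, a 5.2-point gap shifts the unadjusted difference under the null by 0.052 × (35 − 14.7) = 1.06 points. The standard error there is √(2×0.20×0.80/154) = 4.6 points. Larger gaps shift it more. Simulated type I error within the 32% of trials (800,000 trials per scenario):

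| Placebo risk by band | Unadjusted, excess 4-6 L on naltrexone | Unadjusted, excess on placebo | Stratified |
|---|---|---|---|
| 15/20/28% | 3.4% | 7.2% | 5.0-5.1% |
| 10/20/35% | 2.3% | 9.2% | 5.0-5.1% |

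At 10/20/35%, a true 10-point difference averages 8.8 or 11.2 points unadjusted, and 9.9 to 10.0 stratified. With the excess on naltrexone, unadjusted power is about 71% and stratified power about 81%.

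**7. A larger trial.** At an assumed 200 per arm, unadjusted power is 88.3% to 88.6% and stratified power 88.2% to 93.3%. The top of that range needs the most extreme gradient. Section 3.1 does not say how many of the 500 are to be randomised.

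**The case against.** Nothing here is broken. An unadjusted two-proportion test is a legitimate choice for a single-centre trial meant to lead to a larger one, and its 5% error already allows for chance imbalance. The rates of 2.3% and 9.2% are conditional on an imbalance in one direction; averaged over both they are (2.3 + 9.2)/2, about 5.8%, and over all trials 5%. The gain rests on assumed inputs and is about 0 to 1 point unless the gradient is steep; +6.6 needs an odds ratio above 36. A stratified sensitivity analysis would reveal an imbalance without replacing the primary test. Making a Mantel-Haenszel difference primary also separates the primary estimate from the Bayesian estimates planned for the other binary outcomes.

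Most of this stands as a limit on size. It does not remove the case. The trial is randomised once, so its behaviour given the imbalance it actually gets is relevant, and the price of protection is a few tenths of a point of power. A sensitivity analysis alone would leave two answers, with the primary one still uncorrected. Two caveats stand in full. Stratifying corrects differences between bands, not within a band or in other factors. And if progression is read literally as any increase in oxygen, the gradient could weaken or reverse. A reversed gradient still gives a gain; a vanished one leaves only the small loss.

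**Conclusion.** This is an optional improvement, not a defect. The planned test keeps its stated error rate and power. Stratifying by starting oxygen keeps the error rate and changes power by about -0.3 to +6.6 points under the assumed main mix, with 0 to +1 the realistic expectation for mild to moderate gradients. It holds type I error near 5% in the roughly one trial in three with a notable imbalance between bands. The size depends on the assumed mix and risks, none of which the documents supply. The recommendation itself does not depend on the direction of the gradient. Confidence is medium because the prognostic strength of starting oxygen is unknown.

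**What to change.** 1. Before unblinding, name one primary test: a one-sided 0.05 CMH test stratified by the last oxygen level recorded before randomisation, the value used to check the 6 L limit. Use three bands: room air; up to 3 L; more than 3 and up to 6 L.
2. Report the Mantel-Haenszel risk difference with a two-sided 90% interval, which matches the one-sided 0.05 test.
3. Keep the Pearson test and the Jeffreys-prior difference as sensitivity analyses. The latter keeps a primary-outcome estimate on the same footing as the other binary outcomes.
4. Reconcile the two wordings of the primary outcome in the Measurements of Outcomes and Statistical Analysis sections, so that strata and outcome refer to the same scale.

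The cost is SAP wording, a few lines of code, and one field for the oxygen value checked at eligibility, because the daily record covers the previous calendar day. No extra patients or procedures are needed. If starting oxygen proves uninformative, about 0.3 to 0.4 points of power are lost.
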